4. OBJECTIVES*

In this study, we will develop Vaper-to-Vaper (V2V), a suite of mobile peer driven tools, including peer texting and coaching, based on lessons learned in our prior tobacco intervention work. These tools will engage and help adolescents use strategies to manage cravings and successfully quit e-cigarettes. The specific aims of the V2V study are to:

Aim 1: Adapt the existing peer-driven and gamification mobile tools to develop the V2V intervention.

1A. Conduct a qualitative study to (1) explore issues unique to e-cigarette use (e.g., concerns, motivations, triggers, symptoms of nicotine dependence), and (2) understand perceived needs for cessation support (preferences for technology (e.g., texting, app-based) to inform adaptation of the toolset.

1B. Work with these users to build the V2V innovations, including peer messaging for adolescents, peer-to-peer videos, and game narratives for gamification.

1C. Refine the V2V mobile toolset with iterative usability testing (mini-pilot).

There are no hypotheses for Aim 1. Aim 1 is just to adapt the existing peer-driven and gamification mobile tools to develop the V2V intervention.

Aim 2: Evaluate the feasibility of the research protocols and the feasibility and acceptability of the V2V intervention (peer messaging, peer coaching, and gamification) compared to e-cigarette cessation written materials (control) in a pilot feasibility study.

2A. Assess the feasibility of the research protocols, including participant recruitment and retention.

***Hypothesis H1:** We will be able to recruit 80 adolescents (20/school, 40 per study condition), and $\geq 85\%$ will be retained in each study condition at 6-month follow-up.*

2B. Monitor V2V engagement (e.g., number of responses to texting quizzes, peer coaching interactions, peer videos viewed) and assess acceptability of and satisfaction with the program.

2C. Assess preliminary effect size estimates of the V2V intervention on cotinine-validated 7-day point prevalence abstinence, time to first quit attempt, and amount of use.

***Hypothesis H2:** The intervention will be associated with greater cotinine-validated 7-day point prevalence vaping abstinence rates, lower time to first quit attempt, and less amount of e-cigarette use compared to control at 6-month follow-up.*

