10. STUDY ENDPOINTS*

The primary outcome for Aim 2 is the feasibility of the research protocols, including participant recruitment and retention. Secondary outcomes include: preliminary effect size estimates of the intervention on cotinine-validated 7-day point prevalence abstinence, time to first quit attempt, and amount of use; acceptability of and satisfaction with the intervention; system use and adoption of cessation supporting strategies; Social Cognitive Theory (SCT) constructs; and demographics and tobacco use.

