Enrollment: Interested adolescents whose parents (or legal guardians) have not opted out, or who are 18 or older, will meet with the Research Coordinator in the privacy of the high school nurse's office. The adolescent will not meet with the school nurse. After a brief screening, assent, or informed consent if the student is 18 years of age or older, will be explained such that students understand they have a right to refuse to participate, that their care in the school health clinic and their grades will not be affected by whether or not they decide to participate, and confidentiality will be emphasized. *See also #30, Consent Process.* The screening form will be submitted to the IRB for review and approval prior to use in the study.

Study Activities:

Trial: The control group will be provided written e-cigarette cessation materials. To the intervention group, we will provide access to the V2V toolkit, including access to peer coaches and peer messaging, detail how the peer messages and videos were pre-developed and set expectations for the response time from their peer coaches.

Baseline (study entry) and 6-month follow-up data will be collected from all enrolled Aim 2 participants in the privacy of the school nurse's office. Baseline and 6-month data collection forms will be submitted to the IRB for review and approval prior to use in the study; see Table 2 for a description of data to be collected. We have also included measures in the baseline and 6-month data collection forms to assess psychosocial factors (including the Perceived Stress Scale

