With participant permission, we will collect complete and accurate contact information from the student at baseline, including home address, phone, cell phone, email, and phone numbers of three contacts and best times and days to reach them to maximize retention. A contact sheet will be completed by the participant that will include the above information. Care will be taken to maintain the confidentiality of the student's participation; therefore all students will be asked to provide us with the individuals or contact information where they feel comfortable being contacted by study staff or where they feel assured that the confidentiality of their participation will be maintained. The other contacts provided by the student will not be informed of the student's vaping status. We have found in prior studies that cell phone numbers and e-mail addresses are particularly helpful in remaining in contact with this population. Tracking procedures will be implemented for any student who does not attend a scheduled study visit or who is not accessible by telephone or e-mail at the contact location provided. Attempts to locate students will be made mainly through the schools and by telephone calls to the contacts provided or directory assistance.

Table 2. Study Assessments, Measures and Data Collection Timing

Variable and Measure	Relevant Aim	Baseline	6-month follow-up
Recruitment: # screened and eligible, # and reasons for refusal	2A	•	
Retention: # of dropouts, reasons for dropping out	2A		•
Engagement (V2V only): # of completed responses to texting quizzes, peer videos viewed, peer coaching interactions	2B		*
Acceptability and satisfaction: Client Satisfaction Questionnaire (CSQ-8) semi-structured interview	2B		•
Cotinine-validated 7-day point prevalence abstinence: saliva samples collected from all; analyzed for those reporting 7-day abstinence; cut-off 11.4 ng/ml	2C		•
E-cigarette use frequency (past 7 and 30 day) and intensity (# days and amount vaped in past 7 and 30 day)	2C	•	•
THC/marijuana and other tobacco use frequency (past 7 and 30 day) and intensity (# days and amount vaped)		•	•
Social Cognitive Theory (SCT) constructs			
Self-efficacy, confidence to quit: Self-efficacy Questionnaire (SEQ-12)		•	•
Demographics and tobacco use			
Demographics: age, gender, socio-economic status, race/ethnicity, grade in school, academic performance		•	•
History of all tobacco use, past and recent quit attempts, cessation strategies used		•	

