Data collection: Data collected from participants will be obtained through interviews, paper and pencil surveys, and collection of saliva samples for cotinine assessment by the Research Coordinator in-person at the school nurse office at baseline and 6-months post-study entry. The student survey and assessment tools for this study will be adapted from our prior adolescent smoking cessation trials and will be submitted to the IRB for review and approval prior to use in the study. Survey and assessment tools are described in Table 2 on page 10 of the ISP. Data confidentiality will be emphasized on the surveys and verbally by the Research Coordinator (see section #30), and by the use of a unique identification number. Data will be entered into the regulated environment through a secure Research Electronic Data Capture (REDCap) form. REDCap is a secure web application for building and managing online surveys and databases that was funded by the National Institutes of Health. REDCap data is also stored in a regulated environment. These files will be deleted after study completion. Portable devices used to collect data (audio and film recordings) will be UMMS-issued devices and files will not be encrypted during the recording, but the recordings will be transferred as soon as possible (i.e.: typically within the same day) to UMMS servers. Once the files are transferred, they will be deleted from the portable devices.

We will conduct biochemical verification using a saliva NicAlert® test (Nymox Corporation), which is a semi-quantitative method that uses a dipstick to measure the level of cotinine in a sample of saliva. The test strip displays the result in seven zones with each zone representing a range of levels of cotinine/smoking (e.g.: zone 0 [0 – 10 ng/mL, a nonsmoker] to zone 6 [>1000 ng/mL, a heavy smoker]). The results are read as 0-6, and as recommended, any value ≥ 1 is considered as tobacco use. Research staff will enter these values into the database, using the participant ID as an identifier, and destroy the samples.

Data Analysis:

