Aim 2C (Cessation Outcomes) *Hypothesis H2: The intervention will be associated with greater cotinine-validated 7-day point prevalence vaping abstinence rates, lower time to first quit attempt, and less amount of e-cigarette use compared to control at 6-month follow-up.* We recognize that there is some controversy about estimating effect sizes from pilot studies. However, we are calculating effect sizes in our study to provide a range, recognizing that there might be uncertainties because of our small sample size. To estimate effect sizes for V2V intervention versus control, between-condition differences over time will be estimated for **cotinine-validated 7-day point prevalence abstinence** using GEE logistic regression with a random effect for school and fixed effects of condition, time point (baseline and 6 months), and their interaction. Missing data is handled using inverse probability weighting. By taking the repeated measurements into consideration, the GEE model is able to increase the power to test the difference in the outcome. COX regression modeling will be used to examine the intervention effect on **time to first quit attempt** adjusting for other covariates. **Amount of e-cigarette use** will be calculated as a reduction from baseline. We will model this reduction using negative binomial regression modeling if the variance of the distribution of risk reduction is over dispersed.

Other information important for the design of a future study includes standard deviations, as well as **preliminary assessment of possible mediators** such as engagement, behavioral capability, and self-efficacy. We will identify important mediators in exploratory analyses. Guided by the conceptual model based on SCT, we will assess effects of intervention on the mediator and the

effects of the mediator on the outcome, controlling for other mediators in the model, and confounders of the mediator-outcome relationship, and then estimate the proportion of the intervention effect explained. Given the limited sample size, conclusions from the mediation analyses will be limited and treated with caution, but modeling will allow us to explore the constructs of SCT and potential predictors towards a larger RCT.

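### Time to first quit attempt has a planned Cox model, but Table 2 records quit attempts at baseline only and nothing schedules a dated attempt after enrolment

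*Combined protocol and SAP*

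**What the plan says.** Section 4 (Aim 2C) sets out to estimate effects on "cotinine-validated 7-day point prevalence abstinence, time to first quit attempt, and amount of use", and H2 predicts a benefit on all three. Section 10 lists the same set among the secondary outcomes: "preliminary effect size estimates of the intervention on cotinine-validated 7-day point prevalence abstinence, time to first quit attempt, and amount of use". For the quit-attempt outcome, section 13 (Aim 2C) says "COX regression modeling will be used to examine the intervention effect on" it, with covariate adjustment. It does not define an attempt, a time origin, a source for the date or a censoring rule.

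For what is collected, the plan points to Table 2 twice. Section 11 (Trial) says of the baseline and 6-month forms "see Table 2 for a description of data to be collected". Section 13 (Aim 2, data collection) says "Survey and assessment tools are described in Table 2 on page 10 of the ISP".

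Only one row of Table 2 names quit attempts: "History of all tobacco use, past and recent quit attempts, cessation strategies used". It has a mark under baseline, none under 6-month follow-up and no entry under relevant aim. The two rows assigned to Aim 2C are cotinine-validated 7-day abstinence, at 6 months, and "E-cigarette use frequency (past 7 and 30 day) and intensity (# days and amount vaped in past 7 and 30 day)", at both visits.

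**The concern.** A Cox model needs two things for each participant: whether a first attempt occurred after enrolment, and when it occurred or when observation ended. A baseline history covers only the time before enrolment, so it supplies neither. If the forms follow Table 2, one of the three H2 outcomes would reach analysis with no event and no time in either arm.

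The study is meant to inform a later, larger trial, and section 13 commits to reporting effect sizes with their uncertainty. This one would be missing. Dates of first attempts cannot be recovered reliably once the 6-month visits are over, so the point matters before those visits.

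**Working it through.** The plan gives no event count, power or precision figure for this outcome, so there is none to reproduce. The check compares the schedule with what the analysis needs.

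**1. Rows of Table 2**

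| Row | Baseline | 6 months |
|---|---|---|
| Recruitment | yes | – |
| Retention | – | yes |
| Engagement (V2V only) | – | asterisk |
| Acceptability and satisfaction | – | yes |
| Cotinine-validated abstinence | – | yes |
| E-cigarette use | yes | yes |
| THC and other tobacco use | yes | yes |
| Self-efficacy | yes | yes |
| Demographics | yes | yes |
| Tobacco history and quit attempts | yes | – |
| Attitudes | yes | yes |
| Stage of change | yes | yes |
| Nicotine addiction (HONC) | yes | yes |

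That is 13 rows. Eleven carry a 6-month mark, counting the asterisk (10 without it). By row label, none of the 11 names quit attempts. The two rows without a 6-month mark are recruitment and the quit-attempt row itself. So 1 of 3 H2 outcomes has no listed post-baseline measure.

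**2. Could the use items stand in?** Taking 6 months as about 183 days (an assumption):

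- 30-day look-back: 30/183 = 16.4% of follow-up.
- Not covered: 183 − 30 = 153 days, and 153/183 = 83.6%.

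A student who tried to quit in month 2 and relapsed would not be seen. Even within the window, days and amount of use do not date an attempt.

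**3. Could another source supply the date?**

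- *Texting quizzes.* Section 11 says they are sent throughout the 6 months, but nowhere does the plan say they ask about quit attempts. Table 2 lists them as a count of completed responses in the V2V arm only, and section 13 (Aim 2B) uses such counts as engagement. As documented, they give the control arm nothing comparable.
- *Six-month interviews.* These are qualitative and coded by theme. Their stated topics are program experience, suggested improvements, conceptual-model constructs and views of the components. Section 11 limits them to intervention participants, whereas sections 9 and 13 include everyone.
- *Stage of change at 6 months.* This gives a participant's current stage, not the date of a first attempt.

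**4. Who would have data if an item were added?** Section 25 plans 85% retention: 80 × 0.85 = 68 students, or 34 per condition, which matches the plan's figures. Then 80 − 68 = 12 students, 6 per condition, would have no 6-month answer.

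**The case against.** The strongest reply is that this shows a measure missing from a table, not data that will go uncollected. Table 2 is not exhaustive: section 11 puts the stress and depression scales on both forms, and the table omits them. The 6-month form is adapted from earlier adolescent cessation trials, goes separately to the ethics board and may already ask about quit attempts. This stands as a limit: the loss is conditional on the form following the table. It does not remove the point, because the text names those two scales but nowhere names a follow-up quit-attempt item. If the item exists, Table 2 is wrong and the event rules are still unstated.

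A second reply is that the texting quizzes run through follow-up and are the natural place to time an event. They could be, but no quit-attempt content is stated and Table 2 records them for one arm only.

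A third is that a mark may have been lost when the table was extracted. This cannot be fully excluded. The row does show the same pattern as the recruitment row, while most neighbouring rows keep two marks. A restored 6-month mark would still not give the date of a first attempt after enrolment.

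Last, this is a pilot, and section 13 itself says that pilots do not give meaningful effect sizes. That limits the consequence and is reflected in the verdict. It is also fair that the 16% figure only rules out a substitute that the plan never proposed, and that attrition would affect any 6-month item.

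**Conclusion.** The concern holds. The schedule and the analysis plan do not fit together: a Cox model is planned for an outcome with no scheduled post-enrolment event or date in either arm. As scheduled, the hazard ratio for 1 of the 3 H2 outcomes cannot be estimated.

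This rests on reading the quit-attempt row as baseline only, and on Table 2 describing the 6-month form for this item. If the form already asks for a dated first attempt, the defect shrinks to an incorrect table and missing event and censoring rules.

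The outcome is secondary and preliminary, and the primary recruitment and retention aim is untouched. The point should be fixed before the 6-month visits.

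**What to change.** - **Measure.** Add to the 6-month survey, worded identically in both arms, whether any quit attempt was made since enrolment, with a stated definition of an attempt, and the date or week of the first one.
- **Schedule.** Add a Table 2 row for it, marked at 6 months under Aim 2C. If the form already has the item, correct Table 2 instead.
- **Analysis.** In section 13, take enrolment as time zero and censor attempt-free participants at the 6-month visit. Treat those without a 6-month survey as missing. Section 13 says "Missing data is handled using inverse probability weighting" when describing the abstinence model; say that it applies here too.
- **Optional safeguards.** Take events only from this common survey item, not from V2V engagement data. This is a precaution, since the documents do not say that those data record attempts. If recalled dates are coarse, use a discrete-time or interval-censored model.

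The cost is one or two items on a survey that all Aim 2 participants already receive, one table row and a few sentences of analysis text. The drawback is that dates recalled over 6 months are imprecise.

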12. DATA AND SPECIMEN BANKING*

N/A

13. DATA ANALYSIS AND MANAGEMENT*

Aim 1:

Data collection: Data collected from participants during Aim 1 will be obtained through semi-structured individual interviews, peer video interviews, a survey and writing/material development sessions. Data confidentiality will be emphasized during the informed assent/consent process with adolescents (see section #30 for more details). Any data captured via the writing sessions and surveys will be entered into the regulated environment through a secure Research Electronic Data Capture (REDCap) form. REDCap is a secure web application for building and managing online surveys and databases that was funded by the National Institutes of Health. REDCap data is also stored in a regulated and secure environment. With the exception of the peer videos, we will retain study records and documents for a period of 3 years after the completion of the study. As peer videos will become part of our V2V multi-modal intervention, we may use them in future iterations of the intervention. Thus, the peer videos will not be deleted at the conclusion of the study. We have noted in the active parental consent form, adolescent assent form, the consent form for adolescents 18 years or older, and the video release form that there is no limit on the length of time we will store the peer videos and that it is possible that we might use the peer videos in future iterations of the V2V Intervention.

Data Analysis:

Data gathered through qualitative interviews will be managed and coded using NVivo 10. An integrated approach to coding will be used, employing a coding start-list based on protocol questions (deductive coding) and open coding driven by emersion in the qualitative data (inductive coding).²⁴ Duplicate coding will be conducted with at least 10% of the interview transcripts and coding comparisons will be run to ensure inter-rater reliability.²⁵ Disputes in coding decisions will be discussed within the research group until resolved. We will continue to test and refine coding until we attain a Kappa $> .80$. NVivo qualitative analysis software will be employed to generate coding reports that summarize participant responses, ideas, and reflections related to relevant research questions.²⁶ Two members of the research team will complete the thematic analysis

Aim 2:

Data collection: Data collected from participants will be obtained through interviews, paper and pencil surveys, and collection of saliva samples for cotinine assessment by the Research Coordinator in-person at the school nurse office at baseline and 6-months post-study entry. The student survey and assessment tools for this study will be adapted from our prior adolescent smoking cessation trials and will be submitted to the IRB for review and approval prior to use in the study. Survey and assessment tools are described in Table 2 on page 10 of the ISP. Data confidentiality will be emphasized on the surveys and verbally by the Research Coordinator (see section #30), and by the use of a unique identification number. Data will be entered into the regulated environment through a secure Research Electronic Data Capture (REDCap) form. REDCap is a secure web application for building and managing online surveys and databases that was funded by the National Institutes of Health. REDCap data is also stored in a regulated environment. These files will be deleted after study completion. Portable devices used to collect data (audio and film recordings) will be UMMS-issued devices and files will not be encrypted during the recording, but the recordings will be transferred as soon as possible (i.e.: typically within the same day) to UMMS servers. Once the files are transferred, they will be deleted from the portable devices.

We will conduct biochemical verification using a saliva NicAlert® test (Nymox Corporation), which is a semi-quantitative method that uses a dipstick to measure the level of cotinine in a sample of saliva. The test strip displays the result in seven zones with each zone representing a range of levels of cotinine/smoking (e.g.: zone 0 [0 – 10 ng/mL, a nonsmoker] to zone 6 [>1000 ng/mL, a heavy smoker]). The results are read as 0-6, and as recommended, any value ≥ 1 is considered as tobacco use. Research staff will enter these values into the database, using the participant ID as an identifier, and destroy the samples.

Data Analysis:

Aim 2A (Feasibility) Hypothesis H1: *We will be able to recruit 80 adolescents (20/school, 40 per study condition), and $\geq 85\%$ will be retained in each study condition at 6-month follow-up.* We will estimate recruitment rates, overall and per condition. Also, for each condition, we will model 6-month retention, using generalized estimating equation (GEE) logistic regression to account for within-school clustering and dependence over time.

Proposed Sample Size. As appropriate for a pilot study, we are estimating our power and sample size based on the feasibility hypothesis (H1). Because pilot studies do not provide meaningful estimates of effect sizes due to the imprecision inherent in small samples, we base our proposed sample size of 40 students per condition (20 per school) on obtaining precision in estimating condition-specific retention rates, providing important information for design and recruitment for the future R01 study. Based on our prior study of adolescent smoking cessation, estimated intra-school correlation=0.01, for a design effect due to within-school clustering of $1 + [0.01 \times (20 - 1)] = 1.19$, and an effective sample size per condition of $40/1.19 = 34$. Based on our prior studies in

adolescents in school settings, we anticipate at least 85% retention. Thus, a conservatively wide 95% exact CI for per-condition retention rate is (68.9%, 95.0%).

Aim 2B (Monitor V2V Engagement and Assess Program Satisfaction) As the trial progresses, we will monitor engagement overall and by participant subgroups (e.g. by gender, race, age) as a formative assessment. Then, as the trial ends, we will also use this information as a component of our summative evaluation. We anticipate that engagement will lead to positive changes in acceptability, and satisfaction, and cessation.

Defining V2V Engagement level: Engagement measures include: Number of intervention assessments completed, peer videos viewed, and peer coaching interactions. To assess each of these, we will first categorize an adolescent's engagement with each component. For example, for intervention assessments, we will calculate percent of assessments completed (number of assessments divided by the total number of assessment opportunities). Second, we will then calculate the median percent complete across the sample and dichotomize into higher engaged (adolescent's percent completed was at the median or higher) or lower engaged (under the median). We will use a similar procedure for the peer videos viewed. Third, for peer coaching, we will use the count of the number of messages to the peer coach. We anticipate that this count could vary considerably, as some will have sent 0 messages and there is no absolute maximum number of messages sent. We will base the higher versus lower engaged based on the distribution (median split or another reasonable quantile). We could then look at the distribution of engagement with each component, and predictors of engagement (by the adolescent's characteristics).

From these three measures, we will create an *engagement summary score*. The range for the summary score would be from 0 to 3 (0 = lower engagement in all 3 measures, 3 = higher engagement in all 3). We will assess the association of this score with the acceptability and satisfaction score using linear mixed modeling. Acceptability and satisfaction scores will be calculated using the Client Satisfaction Questionnaire (CSQ-8). The overall score is calculated by summing the respondent's rating (item rating) score for each scale item. Scores therefore range from 8 to 32, with higher values indicating higher satisfaction. Similarly, we will look for association between summary score and cessation. We recognize that, for these analyses, power will be limited due to the sample, and further we do not have estimates upon which to base estimates for power calculations. These analyses are conducted to guide our future R01.

Aim 2C (Cessation Outcomes) *Hypothesis H2: The intervention will be associated with greater cotinine-validated 7-day point prevalence vaping abstinence rates, lower time to first quit attempt, and less amount of e-cigarette use compared to control at 6-month follow-up.* We recognize that there is some controversy about estimating effect sizes from pilot studies. However, we are calculating effect sizes in our study to provide a range, recognizing that there might be uncertainties because of our small sample size. To estimate effect sizes for V2V intervention versus control, between-condition differences over time will be estimated for **cotinine-validated 7-day point prevalence abstinence** using GEE logistic regression with a random effect for school and fixed effects of condition, time point (baseline and 6 months), and their interaction. Missing data is handled using inverse probability weighting. By taking the repeated measurements into consideration, the GEE model is able to increase the power to test the difference in the outcome. COX regression modeling will be used to examine the intervention effect on **time to first quit attempt** adjusting for other covariates. **Amount of e-cigarette use** will be calculated as a reduction from baseline. We will model this reduction using negative binomial regression modeling if the variance of the distribution of risk reduction is over dispersed.

Other information important for the design of a future study includes standard deviations, as well as **preliminary assessment of possible mediators** such as engagement, behavioral capability, and self-efficacy. We will identify important mediators in exploratory analyses. Guided by the conceptual model based on SCT, we will assess effects of intervention on the mediator and the

effects of the mediator on the outcome, controlling for other mediators in the model, and confounders of the mediator-outcome relationship, and then estimate the proportion of the intervention effect explained. Given the limited sample size, conclusions from the mediation analyses will be limited and treated with caution, but modeling will allow us to explore the constructs of SCT and potential predictors towards a larger RCT.

Brief Interviews for Future Refinements: In addition to the above assessments, we will conduct brief qualitative interviews with all study participants after they have completed six-month follow-up to deepen our understanding of their experience with the V2V program and obtain specific feedback on ways to improve the program for future refinements. We will use the same approach as Aim 1A to analyze these interviews. Data gathered through qualitative interviews will be managed and coded using NVivo¹⁰. An integrated approach to coding will be used, employing a coding start-list based on protocol questions (deductive coding) and open coding driven by emersion in the qualitative data (inductive coding). Duplicate coding will be conducted with at least 10% of the interview transcripts and coding comparisons will be run to ensure inter-rater reliability. Disputes in coding decisions will be discussed within the research group until resolved. We will continue to test and refine coding until we attain a Kappa $>.80$. NVivo qualitative analysis software will be employed to generate coding reports that summarize participant responses, ideas, and reflections related to relevant research questions. Two members of the research team will complete the thematic analysis.

Data Security (Aim 1 and Aim 2)

All persons collecting or handling data will be trained in human subjects' procedures, confidentiality, and privacy protection. All investigators and project staff are required to receive, and complete, Human Subjects and HIPAA training.

All computerized data, excluding data stored in REDCap (Research Electronic Data Capture), will be kept on secured computers or network servers, behind University of Massachusetts firewalls. These data will be accessible only to research staff with approved access, using confidential usernames and passwords. Any paper data will be kept in locked cabinets or a locked file room accessible only by research staff. Data downloaded from REDCap will be stored and secured according to these methods.

Participant confidentiality will be maintained through a number of strategies. Each participant will be assigned a unique study identification number. Subsequent protection of study data will be assured by the use of locked files and password-protected computer databases. A key to link each code with subjects' names and identifiers will be kept separate from the research dataset in a locked filing cabinet in the study office and in a password-protected excel sheet, stored on secure University of Massachusetts computers. This linkage data is necessary to implement the intervention and conduct the study. The linkage data file will be destroyed at the earliest possible time, once data collection is complete and data accuracy are verified.

Film recordings of peer video interviews will be recorded on portable devices, which will be stored in a secure location (locked drawer that only study staff can access). Portable devices will be UMMS-issued devices and files will not be encrypted during the recording, but the recordings will be transferred as soon as possible (i.e.: typically within the same day) to UMMS servers. Once the files are transferred, they will be deleted from the portable devices. We will obtain

assent and active parental consent from adolescents under the age of 18, and written consent for adolescents 18 years of age or older (see also section #30). Peer videos will be made available to study participants via a secure website (example: Vimeo), and will be password protected. As these peer videos will become part of our V2V multi-modal intervention, we may use them in future iterations of the intervention. Thus, the peer videos will not be deleted at the conclusion of the study. We have noted in the active parental consent form, adolescent assent form, the consent form for adolescents 18 years or older, and the video release form that there is no limit on the length of time we will store the peer videos and that it is possible that we might use the peer videos in future iterations of the V2V Intervention.

We will utilize professional transcription services for interview transcription. Recordings will be uploaded to <https://www.sendthisfile.com>, a HIPAA compliant website, to be transferred to a professional transcriptionist. Send This File uses SAS70 type II/SSAE16 compliant data centers to ensure that private data is protected; features of this service include 128-bit Transport Layer Security (TLS) encryption and password protection, among other security precautions. The transcriptionist uses a password to access uploaded materials to Send This File, works on a password-protected desktop computer, and once transcribed and the transcript is received by the client, the transcriptionist deletes the recording. Recordings will be transcribed verbatim without subject identifiers. Once transcripts have been reviewed for completeness and accuracy, recordings will be deleted from the secure network drive and devices, but will remain on the secure website mentioned above for the duration of the study. Transcriptions will be kept in locked file cabinets in locked offices, and on password-protected computers.

All data will be used for research purposes only; published data will not contain any individual identifiers and will be reported in the aggregate.

See also #14, *Provisions to Monitor the Data to Ensure the Safety of Subjects*, #26, *Confidentiality* and #27, *Provisions to Protect the Privacy Interests of Subjects*.

